6.5.4. Primary Endpoints

6.5.4.1. The primary objective will involve completion of up to 125 [¹⁸F]AV-1451 PET scans on returning Wave 1 and 2 DLBS participants. Once these data are collected, data collection will stop.

6.5.5. Secondary Endpoints

Tau deposition will be examined via estimating the SUVr of [¹⁸F]AV-1451 in temporal regions (both left and right) of interest: (1) inferior temporal gyrus, (2) middle temporal gyrus, (3) superior temporal gyrus, (4) entorhinal cortex, (5) parahippocampal gyrus, and (6) fusiform gyrus. Amyloid accumulation will be measured continuously as the SUVr value averaged across eight cortical regions: dorsal lateral prefrontal cortex, orbitofrontal cortex, lateral parietal cortex, posterior cingulate cortex, anterior cingulate cortex, precuneus, lateral temporal cortex, and occipital lobe.

- **6.5.5.1.** Hippocampal volume and regional cortical thickness will be estimated using FreeSurfer (ver. 5.3), with surface parcellation manually edited, when necessary, by our team of experts.
- **6.5.5.2.** Longitudinal declines in brain structures will be measured using linear mixed models with estimated cortical thickness and white matter volumes from waves 1, 2, and 3 as our primary structural measures, BOLD signal from a subsequent memory task, a semantic judgment task, and resting state as our functional measures, and time of scanning entered as an interaction term.
- **6.5.5.3.** Joint effects of tau and amyloid will be examined by including them as an interaction term in a linear mixed-model analysis.
- **6.5.5.4.** Cognitive decline will be assessed using the following constructs: processing speed, episodic memory, working memory, and executive function. Scores on these constructs will be averaged across relevant DLBS tasks and standardized based on performance at the beginning of this longitudinal study (Wave 1).

6.6. SUBJECT ELIGIBILITY

Participants will be eligible to volunteer for this scan if they participated in Waves 1 or 2 of the DLBS. To determine medical eligibility for the scan by the study physician, those who volunteer when contacted will be asked for verbal consent to provide medical information needed for the physician review. At the subsequent PET scanning visit, all participants must sign the consent form to be eligible for the PET study.

6.6.1. Inclusion Criteria

- **6.6.1.1.** Participated in Waves 1 or 2 of the DLBS
- **6.6.1.2.** Adults aged 38 to 96 years old.
- **6.6.1.3.** Subjects must indicate that they are not currently pregnant if they are women of child-bearing potential. Women of child-bearing potential and men must agree to use adequate contraception (hormonal or barrier method of birth control; abstinence) prior to study entry, for the duration of study participation, and for 90 days following completion of therapy. Should a woman become pregnant or suspect she is pregnant while participating in this study, she should inform her treating physician immediately.
 - **6.6.1.3.1.** A female of child-bearing potential is any woman (regardless of sexual orientation, having undergone a tubal ligation, or remaining celibate by choice) who meets the following criteria:
 - Has not undergone a hysterectomy or bilateral oophorectomy; or
 - Has not been naturally post-menopausal for at least 12 consecutive months (i.e., has had menses at any time in the preceding 12 consecutive months).
- **6.6.1.4.** Volumetric Brain MRI Image (T-1 Weighted MPRage) collected as part of DLBS Wave 1, 2, or 3 protocol.
- **6.6.1.5.** Completed at least 9 years of formal education, or the equivalent of freshman year of high school.
- **6.6.1.6.** Fluent English speakers.
- **6.6.1.7.** Tolerate laying 20 minutes on a flat table for the PET scan.
- **6.6.1.8.** Ability to understand and the willingness to sign a written informed consent.

6.6.2. Exclusion Criteria

6.6.2.1. MMSE score lower than 22; all DLBS participants at the time of initial Wave 1 enrollment between 2008 - 2014 had an MMSE score of 26 or above, indicating normal cognitive function. However, in the time interval between

Waves, it is possible that mental capacity may have deteriorated. We will exclude all participants in Wave 3 testing who have an MMSE lower than 22.

- **6.6.2.2.** Taking some types of sedatives, benzodiazepines, or anti-psychotics.
- **6.6.2.3.** Currently undergoing chemotherapy or radiation for cancer.
- **6.6.2.4.** New history of substance abuse.
- **6.6.2.5.** Has a history of drug or alcohol dependence within the last year, or prior prolonged history of dependence.
- **6.6.2.6.** Recreational drug use in past six months.
- **6.6.2.7.** Central nervous systems disease or brain injury that would preclude participation in the study.
- **6.6.2.8.** Psychiatric or neurological disorder that would preclude participation in this study.
- **6.6.2.9.** Has clinically significant hepatic, renal, pulmonary, metabolic or endocrine disturbances which pose safety risk.
- **6.6.2.10.** Has a current clinically significant cardiovascular disease that poses a safety risk.
- **6.6.2.11.** Has a current clinically significant infectious disease or a medical comorbidity which poses a safety risk.
- **6.6.2.12.** Has received or will receive investigational medication within the 30 days of PET/CT scan.
- **6.6.2.13.** Has received or will receive a radiopharmaceutical for imaging or therapy within 24 hours of PET/CT scan.
- **6.6.2.14.** Is a participant who, in the opinion of the investigator(s), is otherwise unsuitable for a study of this type.

6.7. STUDY PROCEDURES

6.7.1. Screening/Baseline Procedures

In the past, participants who participated in this component of the study received an ECG and a separate physician visit where their medical history was reviewed to determine eligibility. In 2019, flortaucepir was approved by the FDA for medical use and there was no requirement for a physician in-person visit or the ECG prior to the scan. Thus, we have incorporated this practice, and in Wave 3 participants will not receive the ECG. In addition, we have eliminated the physician visit to determine eligibility for this study, and instead it will be collected via a phone screening. We can reduce the participant burden for this research scan by eliminating these two events and instead obtaining a verbal waiver of written consent. This will eliminate one visit for every subject by having both the physician review medical information electronically and the subject provide a verbal waiver of consent over the phone to determine eligibility.

Assessments performed for clinical indications (not exclusively to determine study eligibility) may be used for baseline values even if the studies were done before written informed consent was obtained.

All screening procedures will be performed within 30 days prior to registration unless otherwise stated. For participants who will complete their scan over 30 days since their screening date—most often, this is due to having to reschedule their initial appointment—we will confirm whether their medications, medical history (e.g., surgeries), and allergies have changed since their initial screening. Any such changes will be documented, and changes that may affect their eligibility to participate in this study will be submitted to the physician to confirm whether they are still eligible to participate.

The screening procedures include:

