6.4.3. Other Agents

6.4.3.1. Florbetapir F 18

The inclusion of florbetapir F 18 allows us to get a complete picture of the two major markers of AD pathology – tau and amyloid – in healthy adults. Florbetapir F 18 is an FDA-approved radiopharmaceutical that can be commercially obtained and is used to assess amyloid burden in the brain. It is known that amyloid accumulates long before behavioral and cognitive changes manifest. Better characterization of where and when amyloid accrues and its relationship to tau burden and cognitive changes will provide critical knowledge to help assess Alzheimer's disease, treat patients, and develop therapies. To meet this objective, all participants in the study will have undergone Florbetapir F 18 PET scans at three different times approximately 4 years apart over the last 10 years. See Figure 1. The third Florbetapir F 18 PET scan will be acquired prior to acquisition of the third Tau PET scan under a UTSW IRB approved protocol.

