6.7.3. Procedures On Day of Treatment

Participants will complete the in-person visit at UTSW PET Imaging Center. Assessments will be conducted by a study RA, with the PET Injection and PET scan being conducted by a UTSW PET Technologist. An Attending physician will assess the participant's post-scan vital signs and review any evidence for possible adverse events prior to discharge.

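### For scans within 30 days of the phone screen, no written pre-injection step would detect an unplanned or newly arising scan-date or current-status exclusion

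*Combined protocol and SAP*

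**What the plan says.** Two exclusions in 6.6.2 are dated from the scan. Item 6.6.2.12 reads "Has received or will receive investigational medication within the 30 days of PET/CT scan", and item 6.6.2.13 reads "Has received or will receive a radiopharmaceutical for imaging or therapy within 24 hours of PET/CT scan". Others depend on current status: 6.6.2.2 ("Taking some types of sedatives, benzodiazepines, or anti-psychotics"), 6.6.2.3 (current chemotherapy or radiation) and 6.6.2.11 (current significant infection).

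Eligibility is established by telephone. Section 6.7.1 states: "All screening procedures will be performed within 30 days prior to registration unless otherwise stated". It then provides an update check that begins "For participants who will complete their scan over 30 days since their screening date". For that group, "we will confirm whether their medications, medical history (e.g., surgeries), and allergies have changed since their initial screening", and any change that may affect eligibility goes to the physician.

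The Time and Events table marks inclusion/exclusion criteria, medical history, concomitant medications and the physician's eligibility review under Pre-Visit Screen and under no other column. On the scan day, 6.7.3 lists consent, an MMSE if none was done in the last 30 days, a urine pregnancy test where applicable, and vital signs before injection. The physician's role in that section comes later: "An Attending physician will assess the participant's post-scan vital signs". Section 6.8.1.2 agrees, placing physician screening remotely before scheduling and in person before the participant leaves.

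**The concern.** A criterion defined by the scan date can only be settled close to the scan, and current status can change between a phone call and a visit weeks later. The plan accepts this in part: it asks again after 30 days and repeats the pregnancy test on the day. It gives no reason why a change of medication or treatment inside 30 days needs no question.

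The medication history also carries more weight than it once did. Section 6.7.1 removes both the ECG and the in-person eligibility visit. Sections 6.4.2, 6.8.1.1, 6.8.1.3 and 6.9.1.8 all say that people taking QT-prolonging drugs are excluded, and 6.9.1.8 has this determined at physician screening. With the ECG gone, the history taken at the screen is a main remaining safeguard, and a drug started after the call falls outside it. At stake are participant safety and whether the scanned sample meets the plan's own criteria.

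**Working it through.** The plan gives no figure on this point, so there is nothing to reproduce. The check is a comparison of sections and simple date arithmetic.

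**Inputs**
- Look-back for investigational medication: 30 days (6.6.2.12).
- Look-back for another radiopharmaceutical: 24 hours (6.6.2.13).
- Update check: required only if the scan is more than 30 days after screening (6.7.1).
- Content of the update: medications, medical history, allergies (6.7.1).
- Eligibility and medication review: Pre-Visit Screen only (Time and Events table).

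**Step 1: is anything asked again before injection?** Three places could hold such a step: 6.7.3, the scan-day list in Figure 2, and the Visit Pre-dose column of the table. Between them they contain consent, MMSE, vital signs and the pregnancy test. None repeats the exclusions quoted above.

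**Step 2: how much of each look-back falls after the screen?** Let d be the days from screen to scan, with d ≤ 30 so that no update is required.
- Days of the 30-day look-back falling after the screen = d.
- Share of that look-back = d/30.
- The 24-hour pre-scan window lies wholly after the screen whenever d ≥ 1.

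| d (days) | Update required? | Part of 30-day look-back after the screen | 24-hour window wholly after the screen? |
|---|---|---|---|
| 1 | No | 1 of 30 (3%) | Yes |
| 7 | No | 7 of 30 (23%) | Yes |
| 14 | No | 14 of 30 (47%) | Yes |
| 21 | No | 21 of 30 (70%) | Yes |
| 30 | No | 30 of 30 (100%) | Yes |
| 31 | Yes | Depends on when the update is made | Depends on when the update is made |

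**Step 3: does the update close the gap beyond 30 days?** Only in part. Its listed items do not name radiopharmaceuticals or investigational products, and 6.7.1 does not say how near the scan the questions are put.

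**Step 4: do the two 30-day clocks match?** The screening window runs back from registration, which is not dated relative to the scan. The update trigger runs from screening to the scan. The text should say how the two relate.

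**The case against.** The strongest reply is that a 30-day validity period with an update beyond it is a coherent design, and that safeguards remain. Much of this stands, and it limits the point.

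- Items 6.6.2.12 and 6.6.2.13 cover what a person will receive as well as what has been received, so the phone screen can catch planned exposures. Only unplanned or newly arising ones escape.
- Pregnancy is tested on the day and the MMSE is repeated if older than 30 days, so the gap does not extend to every criterion.
- A participant may volunteer a change during consent, and the investigator may exclude or withdraw anyone at discretion (6.6.2.14, 6.7.6).
- Figure 2 mentions physician review of medications and history, and a physician present during and after the scan. Its layout is lost in the text available, so it should not be read as ruling out every clinician contact before injection. However, the table and 6.8.1.2 place the medication review earlier.

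Three stronger readings are tempting but unsupported. A reader might infer that residual florbetapir would contaminate the tau SUVr, because 6.4.3.1 says "The third Florbetapir F 18 PET scan will be acquired prior to acquisition of the third Tau PET scan" and states no minimum interval. But 6.10.1.1 places amyloid PET in previous visits, 6.6.2.13 bars it within 24 hours, and nothing describes same-day scanning. A reader might also infer that adverse-event relatedness would rest on a month-old medication record. But 6.11.4.2 lists concomitant treatment among the source data, and a physician sees each participant before discharge. Finally, a reader might infer that an ineligible participant would inevitably be injected. The documents show only that no written step would detect the change.

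What the reply does not supply is a written question that reaches a change arising inside 30 days.

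**Conclusion.** The gap is real but limited. For a scan within 30 days of screening, up to all 30 days of the investigational-drug look-back, and the whole 24-hour radiopharmaceutical look-back once a day has passed, fall after the only written check. Current-status exclusions are unconfirmed over the same interval. Section 6.7.1 attributes scans beyond 30 days mostly to rescheduling, which suggests that the shorter interval is the usual case among the up to 125 participants.

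The conclusion assumes that 6.7.3, Figure 2 and the table together list every required pre-injection step. The size is an interval, not a count: the documents give neither the distribution of screen-to-scan times nor the rate at which status changes, so no number of affected participants can be stated. This should be corrected as an inconsistency between when the exclusions apply and when they are confirmed. It is not evidence that participants have been harmed or that the tau data are compromised.

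**What to change.** Reconcile 6.6.2, 6.7.1 and the Time and Events table so that the existing exclusions are confirmed when they apply.

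- In 6.7.1, put the existing update questions (medications, medical history, allergies) to every participant after consent and before injection, whatever the interval since screening. Add the two scan-relative exclusions, 6.6.2.12 and 6.6.2.13, by name.
- Mark this under Visit Pre-dose in the table and list it in 6.7.3.
- Send any change to the study physician by the route 6.7.1 already provides, and state how that physician is reached on the day, since the table describes the eligibility review as done by email.
- State how registration is dated relative to the scan.

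This adds no criterion, threshold or clinical rule. The content of the exclusions, and what follows from a positive answer, remain for the sponsor and the study physician.

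The cost is a few minutes for the research assistant already present, one table edit, and an occasional same-day cancellation of a prepared dose. The paid stand-by participant in 6.7.3.10 is provided for no-shows, so that arrangement may offset such cancellations only in part unless it is extended to cover them.

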6.7.2. Screening Procedures

The verbal consent obtained over the phone will be used to obtain relevant medical information for screening prior to full informed consent at the time of the visit. The specific components of the screen are below. All of this information will be reviewed by a study physician to ensure participant safety before enrollment in the PET study.

6.7.2.1. Medical history

Complete medical and surgical history, history of infections and concurrent disease, and neurological disease history

6.7.2.2. Review subject eligibility criteria

6.7.2.3. Review concomitant medications

6.7.2.4. Mini-Mental State Examination (when considered necessary)

6.7.2.5. Physician Review of subject's medical history, eligibility criteria and concomitant medications prior to enrollment

6.7.3. Procedures On Day of Treatment

Participants will complete the in-person visit at UTSW PET Imaging Center. Assessments will be conducted by a study RA, with the PET Injection and PET scan being conducted by a UTSW PET Technologist. An Attending physician will assess the participant's post-scan vital signs and review any evidence for possible adverse events prior to discharge.

6.7.3.1. Informed Consent

Informed consent and HIPAA consent will be completed on the day of the scan before any other procedures are done.

6.7.3.2. MMSE

Participants who have not completed the MMSE questionnaire in the last 30 days will be asked to complete the questionnaire for purposes of this research study.

6.7.3.3. Pregnancy Test

The day of scanning, females that are of childbearing potential will have a urine pregnancy test performed once again. Results of these tests must be negative in order to proceed with the PET scan.

6.7.3.4. Pre-dose Vital signs

Subject's weight, height, supine blood pressure, pulse rate, and respiratory rate will be collected.

6.7.3.5. Adverse event assessment

Participants will be assessed for possible adverse events that occur as a result of study procedures beginning at the time of written informed consent occurred up to the time of the follow-up phone call described in section 6.7.3. See sections 6.8.2 and 6.8.3 for Adverse Event monitoring and reporting.

6.7.3.6. PET Injection

The subject will receive up to a target dose of 370 MBq as a single IV bolus of [¹⁸F]AV-1451. Participant will be assessed for any adverse events.

6.7.3.7. **PET Scan**

Approximately 80 minutes after injection subjects will be placed in the UTSW PET/CT scanner for a 20-minute brain scan. In total, the imaging visit could take up to 180 minutes for the physician to clear the patient for safety. A member of UTSW staff will be nearby during the procedure. The PET/CT scanner at the PET/CT Center will be used to perform scans for this study. Participant will be assessed for any adverse events.

6.7.3.8. Post-dose Vital signs

Subject's supine blood pressure, pulse rate, and respiratory rate will be taken after PET scan is complete.

6.7.3.9. Post-dose Physician visit

A physician will see and discharge the subject. Physician will ascertain any adverse events that occurred during visit.

6.7.3.10 Participant Compensation

Screen Procedure. If participants complete the screen procedures, \$25 will be deposited to their study account which operates as a cash-based bank card.

The Scanning Visit. Participants who go on to be scheduled for the AV-1451 Wave 3 PET Session will be compensated \$200 additional dollars on this card, even if the session is terminated for some reason. The bank card is study-specific card all enrolled participants can use it to withdraw cash or as a credit card. The card can be used as either debit or credit, and participants will be instructed by study personnel on how to use the card.

Travel Costs. If travel exceeds 50 miles, participants will be approved to receive \$0.58.5 a mile for each additional mile. If a participant prefers not to drive, they can arrange transport with an outside source (eg Uber, Lyft, Cab service) and get reimbursed from their receipts, or we can arrange travel with a university approved carrier and charge it directly to our accounts. We will also make flight arrangements if they are necessary.

Serving As A Stand-By Participant. The scanning agent we use is quite expensive and can only be used the day of the scan. For this reason, it is problematic for us if someone does not show up. Just in case this happens, we are paying an extra participant \$100 to be ready to participate in a scan if someone does not show up. Each stand-by participant would sit in the waiting room for 2-3 hours.

6.7.4. Follow-up Procedures

Study personnel will make a follow-up phone call to the participant within 2 to 3 business days after the scan, but no less than 48 hours post injection. The purpose of this

phone call will be to check if participants have experienced any new adverse events since injection on the imaging day.

Furthermore, as the DLBS is a longitudinal study, participants may continue to be contacted every 4 years for study participation for as long as the study is funded.

Evaluations	Pre-Visit Screen	Visit Pre-dose	Visit Dose	Visit PET Imaging	Visit Post-Imaging	2 – 3 days Post-Injection
Inclusion/Exclusion Criteria	X					
Medical / Disease History	Х					
Concomitant Medications	Х					
Physician Review of eligibility via email	Х					
Informed Consent		Х				
MMSE	Х	Х				
Vital Signs ¹		Х			Х	
Pregnancy Test		Х				
[¹⁸ F]AV-1451 Administration			Х			
PET Imaging				Continuous 20- minute scan		
Physician Visit prior to discharge					Х	
Follow-up Phone Call						Х
Adverse Event Assessment			Х	Х	Х	Х

6.7.5. Time and Events Table for [¹⁸F]AV-1451 Study

¹Height and weight will be measured prior to injection on imaging day.

6.7.6. Removal of Subjects from Study

Subjects can be taken off the study treatment and/or study at any time at their own request, or they may be withdrawn at the discretion of the investigator(s) for safety, behavioral or administrative reasons. The reason(s) for discontinuation will be documented and may include:

24

- **6.7.6.1.** Subject withdraws consent (termination of treatment and follow-up).
- **6.7.6.2.** Subject is unable to comply with protocol requirements.
- **6.7.6.3.** Treating physician determines continuation on the study would not be in the subject's best interest.
- **6.7.6.4.** Subject (female) tests positive for pregnancy at any point in the study.

